Specific Aim 3. It is possible that some skin conditions will be more sensitive to JAK inhibition than others. For example, in our experience, AD, the most common of the evaluated conditions among those with T21, is more likely to respond rapidly to JAK inhibition than vitiligo. If this proves to be the case during the initial 10-participant phase, we may revise our inclusion criteria for the remainder of the trial to maximize recruitment of individuals that will experience a clinical benefit within 16 weeks of treatment. It is also possible that we will have responders and non-responders even within the same immune skin condition. Although this would dilute our chances of reaching our endpoints, it could be nonetheless very informative to identify differences in IFN scores, cytokines, metabolites or other clinical variables among the two groups, which would inform the design of follow up trials.

Specific Aim 4. It is possible that changes in cognition may not be discerned during the relatively short time course of treatment. Also, it is possible that not all participants will be able to complete all tasks. However, we have taken steps to minimize these risks associated with a short treatment window by selecting measures that are scalable and highly sensitive to change. We have addressed the attrition concern by selecting measures that are developmentally engaging, brief, and easy to administer, thus reducing threats to validity based on participant motivation issues. Furthermore, to address confounding issues observed in previous DS assessment work, each task specifically minimizes motor, expressive language, and receptive language demands, all areas of pronounced challenge in DS. The proposed assessments, therefore, strike a balance between the most advanced approaches to characterizing cognition while maintaining a high degree of feasibility of administration and minimizing phenotype specific threats to validity and reliability. Nevertheless, during the initial 10-participant phase we will explore other instruments driven by new findings related to DS outcome measure validation.

VII. Data Analysis Plan:

Specific Aim 1. To define the safety profile of JAK inhibition in people with Down syndrome.

Primary Endpoint: Evaluate the safety of Tofacitinib in people with Down syndrome.

Endpoint Definition: no more than two serious adverse events (SAE) *definitely* related to treatment during the 16-week study period (see *Data and Safety Monitoring Plan*).

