Method: This number is based on published safety data for Tofacitinib for the treatment of rheumatoid arthritis in the general population, which indicates a rate of 9.4 SAEs per 100 patient years. Given that our trial aims to enroll 47 participants for 16 weeks of treatment (though we anticipate up to seven participants would be lost to attrition at various times during the treatment course) for a maximum total of 14.5 patient years of treatment, a comparable number of SAEs is 1.36.

Specific Aim 2. To determine the impact of JAK inhibition on the immune dysregulation caused by trisomy 21.

The overall goal of our data analysis plan in this Aim is to define which immune processes dysregulated by T21 can be normalized by Tofacitinib treatment, i.e. returned to values observed in typical people. Importantly, data shown in this proposal demonstrate that we have already defined the directionality and average magnitude of the change between people with and without T21. For example, we determined that IFN scores are significantly higher in people with DS (*Figure 3C*) and expect that Tofacitinib will reduce these values. Whereas some of the features dysregulated by T21 may be normalized by Tofacitinib treatment, others may not, and this will provide an important mechanistic insight to understand the molecular underpinnings of immune dysregulation in DS. Accordingly, the endpoints associated with this Specific Aim focus on effects of Tofacitinib (16 weeks of treatment) on four classes of molecular markers of immune dysregulation:

Primary Endpoint: Change in IFN scores in the transcriptome of white blood cells.

Endpoint Definition: Statistically significant reduction in average IFN scores between baseline and 16 weeks as defined by a two-sided, paired Student's t-test.

Method: To determine the impact of Tofacitinib on IFN scores, a two-sided, paired Student's t-test will be used to compare baseline and 16 weeks of treatment for participants with good compliance with the study drug (2 or fewer missed pills) and without a confounding reported adverse event in the 7 days prior to the Visit 7 endpoint. With 40 participants, we have 80% power to detect an effect size of 0.45 with a p-value <0.05, as calculated by G*Power software.

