Exploratory Research Goal: A more exploratory research goal, not considered part of the primary endpoint, would be to define if there are differences in IFN scores between clinical 'responders' and 'non-responders' as defined by changes in IGA, DLQI, or skin-specific scores as defined in Specific Aim 3 below. It is difficult at this point to estimate how many responders versus non-responders there will be in the study, and hopefully, all participants will see clinical improvement, in which case this exercise will not be necessary. Assuming that half of the participants will see clinical improvement as defined by IGA for example (i.e. 20 responders versus 20 non-responders), we are powered to see an effect size of 0.66 between the two groups.

Secondary Endpoint: Change in levels of circulating cytokines.

Endpoint Definition: Statistically significant reduction in the cytokine score at 16 weeks of treatment as defined by two-sided, paired Student's t-test.

Method: To determine the impact of Tofacitinib treatment on the Cytokine Score values (a composite Z score derived from the measurements of IP10, TNF- α , CRP, and IL6), a two-sided, paired Student's t-test will be used to compare baseline and 16 weeks of treatment for participants with good compliance with the study drug (2 or fewer missed pills) and without a confounding reported adverse event in the 7 days prior to the Visit 7 endpoint. With 40 participants, we have 80% power to detect an effect size of 0.45 with a p-value less than 0.05, as calculated by G*Power software.

Exploratory Research Goals: For an exploratory component of this analysis to test the impact of Tofacitinib on individual plasma cytokine levels (15+ cytokines measured in total, see *Research Strategy*), using a non-parametric Kolmogorov-Smirnoff (KS) test with 40 participants comparing baseline and 16 weeks of treatment, we have 80% power to detect an effect size of 0.47 with a p-value <0.05, as calculated by G*Power software, using FDR correction for multiple testing on 15 cytokines. This investigation will include cytokines isolated from both the blood and non-invasive skin tapes. For the exploratory goal of defining differences between responders and non-responders, assuming that half of the participants will see clinical improvement, we are powered to see an effect size of 0.66 for the composite Cytokine Score and 0.68 for individual cytokines.

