Tertiary Endpoint: Change in levels of neurotoxic metabolites in the kynurene pathway.

Endpoint Definition: Statistically significant reduction in one or more of three kynurenone dysregulation values at 16 weeks of treatment as defined by a two-sided, paired Student's t-test with FDR correction.

Method: To determine the impact of Tofacitinib treatment on the levels of kynurenone, quinolinic acid, and the kynurenone/tryptophan ratio, a two-sided, paired Student's t-test will be used to compare baseline and 16 weeks of treatment for participants with good compliance with the study drug (2 or fewer missed pills) and without a confounding reported adverse event in the 7 days prior to the Visit 7 endpoint. With 40 participants, we have 80% power to detect an effect size of 0.45 with a p-value less than 0.05, as calculated by G*Power software, and using FDR correction for multiple testing on three KYN pathway dysregulation values.

Exploratory Research Goal: For the exploratory goal of identifying differences between clinical responders and non-responders, assuming that half of the participants will see clinical improvement (i.e. 20 responders versus 20 non-responders), we are powered to see an effect size of 0.66 between the two groups, as calculated by G*Power software.

Tertiary Endpoint: Change in levels of autoantibodies associated with AITD and celiac disease.

Endpoint Definition: Statistically significant reduction in levels of one or more autoantibodies at 16 weeks as defined by a two-sided, paired Student's t-test.

Method: To determine the impact of Tofacitinib on levels of autoantibodies associated with 1) AITD, i.e. anti-thyroperoxidase (TPO), anti-thyroglobulin (TG), and anti-thyroid stimulating hormone receptor (TSHr), and 2) celiac disease, i.e. anti-tissue transglutaminase (TG) and deamidated gliadin peptide (DGP), a two-sided Student's t-test will be used to compare baseline and 16 weeks of treatment. With 40 participants, we have 80% power to detect an effect size of 0.45 with an FDR corrected p-value less than 0.05, as calculated by G*Power software.

Specific Aim 3. To define the impact of JAK inhibition on immune skin conditions in Down syndrome.

Secondary Endpoint: Change in IGA, DLQI, and/or disease-specific scores.

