Endpoint Definition: A statistically significant *percentage reduction* in one or more metrics of skin pathology, including: a) IGA values, b) DLQI values, and/or c) disease-specific scores between baseline and 16 weeks as defined by a two-sided, paired Student's t-test.

Method: The first endpoint for this Specific Aim will be to monitor changes in the Investigator's Global Assessment (IGA), which is a well-established, disease-agnostic measurement of skin disease severity that employs a continuous visual analog scale and has good test-retest reliability. A second disease-agnostic secondary endpoint will be the Dermatology Life Quality Index (DLQI), a patient-reported outcome that is commonly used in dermatology trials. The third secondary endpoint for this study is a percentage reduction in the disease-specific measurements used to monitor each skin condition. We will employ Eczema Area and Severity Index (EASI) for AD, Severity of Alopecia Tool (SALT) for AA, Modified Sartorius Score (MSS) for HS, Psoriasis Area and Severity Index (PASI) for psoriasis, and Vitiligo Extent Tensity Index (VETI) for vitiligo. By focusing on a *percentage reduction* in disease-specific scores, we will be able to compare values from participants with different conditions. In every case (IGA, DLQI or disease-specific scores) we will define whether the percentage reduction reaches significance using a two-sided, paired Student's t-test comparing baseline and 16 weeks of treatment. In every case, for 40 individuals, we have 80% power to detect an effect size of 0.45 with a p-value less than 0.05, as calculated by G*Power software. Finally, although we will be analyzing changes between baseline and 16 weeks, data will be also gathered at the intermediate time point of eight weeks for research purposes.

Specific Aim 4. To characterize the impact of JAK inhibition on cognition and quality of life in Down syndrome.

Tertiary Endpoint: Change in any one or more of the cognitive assessments performed.

Endpoint Definition: a statistically significant improvement in any one of the cognitive measures employed between baseline and 16 weeks as defined by a Wilcoxon signed-rank test with FDR correction or a two-sided, paired Student's t-test, as appropriate.

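### The exploratory link between biomarkers and skin response rests on a responder split alone, and for the IFN score the plan wrongly treats it as unnecessary if everyone improves

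*Combined protocol and SAP*

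**What the plan says.** Under Section VII, Specific Aim 2, the exploratory goal for the primary biomarker is to "define if there are differences in IFN scores between clinical 'responders' and 'non-responders' as defined by changes in IGA, DLQI, or skin-specific scores". The plan admits that the number of responders is hard to predict, and adds: "hopefully, all participants will see clinical improvement, in which case this exercise will not be necessary". It then assumes 20 responders and 20 non-responders and gives 0.66 as the detectable effect.

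The cytokine paragraph has the same goal. So does the kynurenine paragraph: "For the exploratory goal of identifying differences between clinical responders and non-responders, assuming that half of the participants will see clinical improvement". Neither repeats the statement that the exercise is unnecessary if all improve.

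For the definition of response the IFN paragraph points to Specific Aim 3. That section says the IGA "employs a continuous visual analog scale" and tests average percentage reduction, but gives no responder cut-off. Section VI, Specific Aim 3, expects that "some skin conditions will be more sensitive to JAK inhibition than others", and says differences between responders and non-responders would help in designing later trials.

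**The concern.** The scientific question is whether biomarker levels track the degree of skin benefit. A two-group comparison answers a narrower question, and it needs members in both groups. If all 40 participants improve, some slightly and some greatly, the data still show whether those with higher IFN scores, or larger falls in IFN score, improved more. The plan would stop looking at that point, which is the outcome it hopes for.

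No other planned analysis fills the gap. The multivariate methods in Section VI look for markers that change on treatment. The repeated-measures ANOVA at the end of Section VII covers age and sex. Correlation of IFN scores with severity appears only as background on such scores.

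There are two further weaknesses. With no cut-off and three candidate measures (IGA, DLQI, disease-specific scores), the split would have to be defined after the fact. And a comparison pooled over conditions with different response rates can mistake a difference in case mix for a biomarker effect.

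**Working it through.** **Inputs from the plan.** 40 participants; power 80% and alpha 0.05 ("we have 80% power to detect an effect size of 0.45 with a p-value <0.05"); two-sided, as for the parent endpoint; an assumed 20/20 split; effect size 0.66. Alpha and sidedness are not restated for the responder comparison and no test is named there, so I carry them over and use a two-sample t-test.

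**The plan's own figures.** A paired t-test with n = 40 and d = 0.45 has 79.3% power (80% detectable d = 0.454), so the parent figure reproduces. The 0.66 does not reproduce as a 20 versus 20 comparison. The noncentrality is 0.66 × √(20 × 20/40) = 2.09 on 38 df, which gives 53.0% power; the 80% detectable d is 0.909. The value 0.66 matches a paired test with n = 20. That is a separate error. Here 0.66 serves only to place the plan's effect size on the correlation scale.

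**Conversion.** At an even split, the point-biserial correlation is d/√(d² + 4) = 0.66/√4.4356 = 0.313. Dividing by √(2/π) = 0.798 gives an underlying correlation of 0.393.

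**Graded relation.** I simulated bivariate normal biomarker and skin change with n = 40 and two-sided 0.05. The Pearson test is compared with a t-test after ranking on skin change and splitting. The correlation is assumed; the documents give none.

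| Correlation | Continuous | Split 20/20 | Loss | Split 36/4 | Loss |
|---|---|---|---|---|---|
| 0.20 | 23.5% | 16.4% | 7.1 | 10.6% | 12.9 |
| 0.30 | 48.1% | 32.2% | 15.9 | 18.1% | 30.0 |
| 0.393 | 72.5% | 51.5% | 21.0 | 28.5% | 44.0 |
| 0.45 | 84.8% | 64.3% | 20.5 | 36.2% | 48.6 |
| 0.50 | 92.2% | 74.8% | 17.4 | 43.0% | 49.2 |

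A repeat run at 0.393 gave 73%, 52% and 27%, so the 36/4 loss there is about 45 points. Results for 36/4 and 4/36 are the same. At 40/0 the split cannot be run, while the continuous analysis is unaffected because it uses no cut-off.

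**Two-class response.** Suppose instead that there are two true classes with skin change 3 SD apart and a biomarker difference of d = 0.9. If class membership were known without error, the split would win: 79% against 63% at 20/20, and 38% against 20% at 36/4. If participants are split on the observed score, as they would be in practice, the gain is about 4 to 8 points. At 2 SD separation or less, the split loses or roughly ties at 20/20.

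**Case mix.** Assume five conditions of 8 participants, response rates of 85/60/40/70/10%, and no link within condition. With a between-condition IFN SD of 0, 0.5, 0.7 and 1.0 within-condition SD, the pooled test rejects about 5%, 10%, 13% and 18% of the time. With rates of 30 to 70% it rejects 5 to 9%. A model with condition as a factor stays near 5%. All of these inputs are assumptions.

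**Cost of adjusting.** At a within-condition correlation of 0.43, power is 81% unadjusted and about 76 to 77% with a five-level condition factor.

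**The case against.** The strongest reply is that this is labelled exploratory and outside the primary endpoint. It decides no endpoint, stopping rule or sample size, and a correlation could be run later on the same data. That stands, and it limits the weight of the point. It does not rescue the stated inference, and pre-specifying the model is better than choosing a responder cut-off once results are known.

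A second reply is that the power loss depends on assuming a smooth gradient, while Section VI contemplates distinct responders and non-responders within a condition. This stands in part: with widely separated classes the split can do better. The reversal is large only when class membership is known without error.

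A third reply is that the plan names no test and does not rule out adjustment, so the case-mix result describes an assumed analysis. That also stands. It is a risk, not a demonstrated bias.

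Three stronger readings are tempting and are not supported:
- A reader might infer a fixed loss of 20 to 49 points. That range needs a correlation of about 0.45 and splits from 20/20 to 36/4, and neither is in the documents.
- A reader might infer that the method fails chiefly when most participants respond. The loss is symmetric; only the statement that the exercise is unnecessary is specific to high response.
- A reader might infer that the plan drops all three biomarker analyses if everyone improves. It says so for the IFN score alone. For cytokines and metabolites the comparison simply could not be run.

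**Conclusion.** The point holds as a correction to an exploratory analysis. Without any outside figure, it is established that the responder split is the only planned link between biomarkers and skin response, that no cut-off is defined, and that the reason given for skipping the IFN analysis is wrong.

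The size of the power loss is conditional on a graded, roughly bivariate normal relation. Over assumed correlations of 0.2 to 0.5 it is about 7 to 21 points at 20/20 and 13 to 49 points at 36/4. At the correlation matching the plan's 0.66 it is 21 and about 45 points. The case-mix rejection rate of about 5 to 18% cannot be narrowed, because the documents give no between-condition IFN spread. No endpoint conclusion changes.

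**What to change.** In the exploratory paragraphs of Section VII, Specific Aim 2 (IFN score, Cytokine Score, kynurenine values):

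- Make the planned analysis a linear model of baseline-to-week-16 change in the continuous IGA on the biomarker. Fit the baseline value and the change in the biomarker in separate models.
- Include the primary qualifying skin condition as a factor. Assign one per participant, because the protocol admits people with more than one, and group rare conditions as other.
- Delete the clause saying the exercise will not be necessary if all improve.
- Keep the responder split as a descriptive display.

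The cost is wording only: no added visits, samples or participants. The condition factor takes about 4 to 5 points of power in the example above, and results are reported as slopes instead of a responder contrast.

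### The 0.66 detectable effect for responders versus non-responders is the paired value for n=20; two independent groups of 20 need about 0.91

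*Combined protocol and SAP*

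**What the plan says.** All the figures are in section VII, Data Analysis Plan.

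- **IFN score, Method (primary).** Two-sided paired t-test: "With 40 participants, we have 80% power to detect an effect size of 0.45 with a p-value <0.05, as calculated by G*Power software".
- **IFN score, Exploratory Research Goal.** If half the participants improve: "i.e. 20 responders versus 20 non-responders), we are powered to see an effect size of 0.66 between the two groups". No test, sidedness, alpha or power is given in that sentence.
- **Cytokines, Exploratory Research Goals.** For the responder split: "we are powered to see an effect size of 0.66 for the composite Cytokine Score and 0.68 for individual cytokines". For change over time in 15 individual cytokines the plan names a test, "using a non-parametric Kolmogorov-Smirnoff (KS) test with 40 participants comparing baseline and 16 weeks of treatment", and says "we have 80% power to detect an effect size of 0.47 with a p-value <0.05, as calculated by G*Power software, using FDR correction".
- **Kynurenine values.** The Method gives 0.45 at n=40, "and using FDR correction for multiple testing on three KYN pathway dysregulation values". The exploratory goal repeats "we are powered to see an effect size of 0.66 between the two groups, as calculated by G*Power software".
- **Autoantibodies, Method.** "80% power to detect an effect size of 0.45 with an FDR corrected p-value less than 0.05".
- **Specific Aim 4, Method.** CANTAB is given 0.45 with an FDR-corrected p-value. The Leiter 3 subdomains are given 0.32 by Wilcoxon signed-rank, also with an FDR-corrected p-value, but without n, sidedness or parent distribution.

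**The concern.** A responder/non-responder comparison is between two independent groups, yet the figure attached to it is the one a paired or one-sample test would give with 20 people. The Specific Aim 3 part of section VI (Potential Scientific Problems) says such differences would inform the design of later trials. A null result read against a claimed sensitivity of 0.66 would suggest that differences of that size had been looked for with adequate power, when they would be missed about half the time.

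A lesser question is whether the multiplicity correction named beside several other figures entered the calculation at all, because the same 0.45 is quoted for a single uncorrected test and for families of tests.

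**Working it through.** **Inputs.** n=40, 80% power, alpha 0.05, two-sided, paired t (IFN score Method). Groups of 20 and 20, stated effects 0.66 and 0.68 (exploratory goals). Alpha, sidedness and power for the responder comparison are assumed to carry over from the IFN score Method.

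**Method.** Power comes from the noncentral t distribution.
- Paired or one-sample: noncentrality = d × √n, df = n − 1.
- Two groups: noncentrality = d × √(n₁n₂/(n₁+n₂)), df = n₁ + n₂ − 2.
- Rank tests: the same formulas with n multiplied by the asymptotic relative efficiency (3/π for a normal parent, π²/9 logistic, 1.5 Laplace).

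**Step 1: reproduce the plan's n=40 figures.**
- Paired t: 80% power needs noncentrality 2.873, so d = 2.873/√40 = 0.454. The plan's 0.45 reproduces.
- Signed-rank, normal parent: effective n = 40 × 3/π = 38.2, d = 0.465. This is the plan's 0.47.

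**Step 2: the same two calculations at n=20.**
- Paired t: noncentrality 2.954, d = 2.954/√20 = 0.660. This is the plan's 0.66.
- Signed-rank, normal parent: effective n = 19.1, d = 0.678. This is the plan's 0.68.

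All four figures therefore come out of the one-sample/paired family, with n halved for the responder split.

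**Step 3: the comparison actually described, 20 versus 20.**
- √(20×20/40) = 3.162 and df = 38. 80% power needs noncentrality 2.875, so d = 2.875/3.162 = 0.909 (one-sided 0.801).
- Mann-Whitney, two-sided, normal parent: 0.932.
- 0.909/0.660 = 1.38, so the detectable effect is 38% larger than stated.

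**Step 4: power at 0.66, two-sided t-test.**

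| Split | Noncentrality | Power at 0.66 | Effect for 80% power |
|---|---|---|---|
| 20/20 | 0.66 × 3.162 = 2.087 | 53% | 0.91 |
| 15/25 | 0.66 × 3.062 = 2.021 | 50% | 0.94 |
| 10/30 | 0.66 × 2.739 = 1.807 | 42% | 1.05 |

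With 37 per group power at 0.66 is 79.98%, and with 38 it is 81.0%. So 80% needs 38 per group, 76 in total, against 40 planned completers.

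**Step 5: figures with FDR wording.** The 0.45 for kynurenine, autoantibodies and CANTAB equals the uncorrected 0.454 of step 1. The 0.47 equals the uncorrected signed-rank 0.465, although the sentence names a Kolmogorov-Smirnov test. Simulating Benjamini-Hochberg at d = 0.45, n = 40, with independent tests, the chance of finding at least one responding marker is:

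| Markers that respond | Chance |
|---|---|
| 3 of 3 | 96% |
| 2 of 3 | 88% |
| 1 of 3 | 64% |
| 2 of 5 | 82% |
| 1 of 5 | 57% |

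**Step 6: Leiter 0.32.** Signed-rank at n=40, uncorrected. Two-sided: 0.368 (Laplace), 0.433 (logistic), 0.465 (normal), 0.491 (minimum efficiency). One-sided: 0.325, 0.381, 0.410 and 0.432 in the same order. Only the one-sided Laplace setting (0.3247 unrounded) rounds to 0.32.

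**The case against.** **The settings are not stated, so 0.91 is conditional.** This stands. Other two-group choices give smaller values: two-sided Mann-Whitney with 20 per group needs 0.866 with a logistic parent and 0.736 with a Laplace parent. The nearest to the plan's figure is one-sided Mann-Whitney with a Laplace parent, at 0.650. That still misses 0.66 and departs from the two-sided t-tests used throughout the plan. The paired n=20 explanation matches both 0.66 and 0.68. A within-group reading would rescue 0.66, but the text says the effect is between the two groups.

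**The comparison is hedged.** This also stands. The plan calls it exploratory, keeps it outside the primary endpoint, says the split is hard to predict and allows that it may not be needed. That limits the importance of the error but does not make the figure right.

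**Stronger readings that the documents do not support.**
- A reader might infer that every FDR-labelled figure is wrong. For autoantibodies and CANTAB the correction is attached to the p-value itself. In the cytokine and kynurenine sentences it may describe only the planned analysis. Where success means one or more markers, power can stay above 80% after correction (step 5).
- A reader might put a single number on the Kolmogorov-Smirnov mismatch, such as 34% power at 0.47 or about 0.8 SD needed for 80%. Those treat a paired effect as a shift between independent samples. Holding the paired effect at 0.47, simulated power is about 64%, 31%, 11% and 4% at within-person correlations of 0, 0.5, 0.7 and 0.8. The documents give no correlation, so only the range can be stated.
- A reader might call the Leiter 0.32 an error. One setting reproduces it, and the plan attaches two-sidedness to the t-test, not to the Wilcoxon test. It is a matter for disclosure.

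**Conclusion.** The responder figures are wrong as written. At two-sided 0.05 and 80% power, 20 versus 20 detects 0.91 by t-test, not 0.66, and power at 0.66 is about 53% at best, because an uneven split lowers it. For individual cytokines the corresponding value is about 0.93 by Mann-Whitney with a normal parent, before FDR, in place of 0.68. This rests on carrying alpha, sidedness and power over from the IFN score calculation. That the paired formula was used is inferred from the numerical match.

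The FDR labels, the test behind 0.47 and the Leiter settings are clarifications, held with less certainty. It would be a mistake to conclude that the trial's sizing is affected: the primary 0.45 is correct, and the responder, kynurenine, autoantibody, individual-cytokine and cognitive items are all exploratory or tertiary.

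**What to change.** 1. In the exploratory goals for the IFN score, Cytokine Score and kynurenine values, name the two-group test and its settings and replace 0.66 with 0.91 (two-sided t-test, 0.05, 80% power, 20/20). It would help to add that 15/25 and 10/30 splits need 0.94 and 1.05.
2. For individual cytokines, name the two-group test and replace 0.68 with its value before FDR (about 0.93 for Mann-Whitney with a normal parent).
3. Label the 0.45 (kynurenine, autoantibodies, CANTAB) and the 0.47 (15 cytokines) as uncorrected per-test figures. Name the test that 0.47 belongs to, or recompute it for the test to be used.
4. For Leiter, state n, sidedness and parent distribution and drop the FDR label, or recompute. Two-sided with a normal parent at n=40, for example, gives about 0.47 before FDR.

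The cost is a text correction. Endpoints, visits and sample size stay as they are, and the stated sensitivity of the responder comparison becomes less favourable.
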